4.1.3. Data capture methods and storage

All data collected is be saved databases using Microsoft Excel and IBM SPSS Statistics. The files are be stored encrypted on our department's file servers. Patient identifiers are stored in a separate file. All data and records generated throughout the course of the study are kept confidential. Only the study investigators have access to the data. In case of publication of the studies results patients personal information will be kept confidential.

5. Statistical analysis

Translations in the x (medial-lateral), y (superior-inferior) and z (anterior-posterior) directions as well as rotations around the x (transversal), y (longitudinal) and z (sagittal) axes are analysed. The resulting 3DV is calculated as follows:

$$3DV = \sqrt{x^2 + y^2 + z^2}$$

IBM SPSS Statistics 22 (IBM Cooperation, Armonk, NY, USA) is used for statistical analysis To evaluate the correlation between the time elapsed since the first measurement in each treatment session and the 3DV, Spearman's rank correlation coefficient is calculated. An analysis of variance (ANOVA) is used to analyse this correlation further. A p value of < 0.05 is deemed to be significant.

6. Ethical considerations

The study is conducted in accordance with the ethical standards of the 1964 Helsinki Declaration and its later amendments. There is no risk involved for the participating patients. All parameters and measurements required for the study are routinely collected as part of the treatment. All patient data is kept confidential and the rights and welfare of the enrolled patients is not adversely affected. Every patient is informed about the analysis of data collected over the course of the treatment. Written informed consent for this analysis is obtained. While there is no direct benefit for the patients participating in the study, results from the study will help improve treatment for future patients treated in our department. Information about the accuracy of treatment and the extent of patient motion during treatment sessions is vital in order to determine the necessary safety margins used in

treatment planning. If patient motion is found to significantly exceed 1 mm an additional safety margin will be implemented.

7. Literature

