CLINICAL TRIAL PROTOCOL

**Intrafractional 6D head movement during stereotactic intracranial
radiation therapy with thermoplastic mask fixation**

A prospective observational study

Version: 1.0

Date: 25.01.2019

Principal Investigator

Ao.Univ.[name]. [name]
Universitätsklinik für Strahlentherapie-Radioonkologie
Medizinische Universität Innsbruck
[name]
[name]

Sponsor

Medical University Innsbruck
[name]
[name]
[name]

1. Study Summary

Title	Intrafractional 6D head movement during stereotactic intracranial radiation therapy with thermoplastic mask fixation
Study Center	single center Department of Therapeutic Radiology and Oncology Innsbruck
Study Design /Methodology	A prospective observational study
Objectives	to investigate intrafractional head motion during stereotactic intracranial radiation therapy with non invasive thermoplastic mask fixation with repeated X-ray position verification during RT sessions.
Endpoints	3D deviation of head position, rotational and translational deviations. Development of head deviation with time during single RT sessions
Number of Subjects	5
Eligibility Criteria	Male and female patients with a single intracranial solid tumour. Stereotactic radiation therapy with immobilization by non invasive thermoplastic mask.
Study Interventions and Measures	repeated X-ray position verification during RT sessions
Statistical Methodology	calculation of 3D deviation from X, Y, Z translational deviation. Descriptive statistics of 3D, translational and rotational deviation. Analysis of time dependent deviation with Spearman's correlation. ANOVA Analysis of deviations in 2-minute interval groups.

2. Introduction

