2.3. Study objectives

The purpose of the present study is to evaluate the precision and reliability of mask fixation of the head during the entire duration of stereotactic RT sessions. In order to assess position accuracy not only at the beginning and the end of the sessions, we repeatedly map deviations of the head position in both translation and rotation, by concomitantly measuring intrafractional movement using the ExacTrac 6D X-Ray Positioning System (Brainlab AG, Munich, Germany). From the obtained data we evaluate the need to adjust safety margins around the gross tumor volume (GTV) whenever the investigated thermoplastic mask is used instead of invasive ring fixation.

3. Study design and Methods

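### Section 5 names only the translation-based 3DV for the time analyses, and nothing says how the recorded rotations enter a margin evaluation stated in millimetres

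*Combined protocol and SAP*

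**What the plan says.** The Study Summary (Section 1) gives as endpoints "3D deviation of head position, rotational and translational deviations" and then "Development of head deviation with time during single RT sessions". For methods it lists "Descriptive statistics of 3D, translational and rotational deviation", "Analysis of time dependent deviation with Spearman's correlation" and "ANOVA Analysis of deviations in 2-minute interval groups". The last two name no variable.

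Section 2.3 states the aim: "we repeatedly map deviations of the head position in both translation and rotation". The data so obtained are then to inform whether margins around the GTV need adjusting.

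Section 4.1.2 extracts three translations and three rotations per measurement and derives the 3D deviation from the translations. Section 5 gives the formula, 3DV = √(x² + y² + z²). It says that rotations are analysed too, without giving a method. Spearman's coefficient is then calculated "To evaluate the correlation between the time elapsed since the first measurement in each treatment session and the 3DV", and the ANOVA is described as a further look at that correlation.

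Section 6 contains the only action statement: "If patient motion is found to significantly exceed 1 mm an additional safety margin will be implemented". It names no variable, summary or test.

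**The concern.** The title announces six dimensions and six are recorded, but the one composite measure and the one detailed time analysis use three. Read on its own, Section 5 leaves any trend in rotation over the session untested.

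The margin question makes this more than a matter of presentation. A margin has to cover the edge of the target, and the edge moves when the head rotates even if the isocentre stays still. Rotations summarised in degrees cannot be set against a statement in millimetres unless they are converted, and the plan has no conversion. Section 3.3.2 also says that positions are not corrected during a session, so rotation that develops within it is not removed by the procedure.

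**Working it through.** The protocol states no derived figure on this point, so there is none to reproduce. The check compares the sections and then sizes the gap by geometry.

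**Comparison of sections**

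| Item | Study Summary | Section 5 |
|---|---|---|
| Rotations | endpoint; descriptive statistics | analysed, method not stated |
| Spearman | deviation over time, variable not named | 3DV only |
| ANOVA | deviations in 2-minute groups, variable not named | follow-up of the 3DV correlation |
| Conversion from degrees to mm | none | none |

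**Inputs**
- 1 mm: Section 6.
- Deviations refer to the target isocentre: Section 3.3.2. I assume that the recorded rotations are expressed about that point.
- Distance r from isocentre to target edge: not in the documents; assumed 10, 20 and 30 mm. Section 3.2.1 requires a single lesion, which limits r but does not fix it.
- Intrafraction rotation θ: not in the documents; assumed 1 and 2 degrees. Section 3.3.2 has a 1.0 degree set-up limit, but this applies before the reference image is taken, so it serves only as a scale.

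**Step 1. Pure rotation.** With x = y = z = 0, 3DV = 0 for every θ. A point at distance r, on a line at right angles to the rotation axis, moves d = 2r·sin(θ/2).

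| θ | r = 10 mm | r = 20 mm | r = 30 mm |
|---|---|---|---|
| 1 degree | 0.17 mm | 0.35 mm | 0.52 mm |
| 2 degrees | 0.35 mm | 0.70 mm | 1.05 mm |

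For example, 2 × 20 × sin(0.5°) = 40 × 0.00873 = 0.35 mm. One degree about each of the three axes is a total angle of 1.73 degrees, and gives 0.30, 0.60 and 0.90 mm. Rotation alone reaches 1 mm at r = 57 mm for 1 degree and at r = 29 mm for 2 degrees.

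**Step 2. Rotation with translation.** Take a sphere of radius r around the isocentre. Its largest displacement is between √(3DV² + d²), when the translation lies along the rotation axis, and 3DV + d, when it is at right angles to that axis. The 3DV values below are hypothetical; θ = 1 degree.

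| 3DV | r = 10 mm | r = 20 mm | r = 30 mm |
|---|---|---|---|
| 0.7 mm | 0.72 to 0.87 | 0.78 to 1.05 | 0.87 to 1.22 |
| 0.9 mm | 0.92 to 1.07 | 0.97 to 1.25 | 1.04 to 1.42 |

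At 3DV = 0.7 mm and r = 10 mm, even the upper bound stays below 1 mm. At 20 and 30 mm the range straddles 1 mm. At 3DV = 0.9 mm the range straddles 1 mm at 10 and 20 mm and lies wholly above it at 30 mm.

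**The case against.** The strongest reply is that rotation is not left out. It is extracted, summarised descriptively, and said in Section 5 to be analysed. The Study Summary's time analyses speak of deviation in general and can be read to include rotation. The time endpoint mentions head deviation, not rotational deviation, so an analysis of 3DV is one fair reading of it. The 1 mm sentence refers to patient motion, not 3DV. The sizes rest on assumed radii and angles, and the combined upper bounds need a particular geometry.

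Most of this stands, and it rules out three stronger readings that a reader might infer:

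- *The plan ignores rotation, or treats a rotating head as still.* This is true of 3DV only. The rotation summaries would show the movement.
- *The plan cannot detect rotational drift.* Section 5 does not name such an analysis, but the Study Summary's wording allows it. What the documents show is an unresolved difference between two sections.
- *The margin conclusion will miss rotational displacement.* The 1 mm statement is not tied to 3DV, and Section 2.3 draws on both kinds of data. The rule is undefined, which is not the same as being limited to translation.

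The reply does not supply a variable list for the time analyses, or any route from degrees to millimetres.

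**Conclusion.** The point holds as a gap in specification. Section 5 and the Study Summary differ on what the time analyses cover, and no text says how rotation bears on a judgement made in millimetres. 3DV alone understates displacement at the target edge by an amount that depends on target size and rotation, neither of which the documents give. Under the assumptions above, 1 degree adds at most 0.17 mm at 10 mm and at most 0.52 mm at 30 mm. This is minor for a small target with 3DV well below 1 mm. It can change the comparison with 1 mm, but need not, when the target is larger, the rotation is larger or about several axes, or 3DV is already close to 1 mm. It is a worthwhile, inexpensive improvement and not the correction of a demonstrated error in a result.

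**What to change.** Three changes to Section 5:

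1. Reconcile it with the Study Summary by naming the variables for Spearman and ANOVA, and add rotation magnitude, labelled exploratory. Use the total rotation angle, or the absolute rotation per axis. Signed values will not do, because drifts in opposite directions can cancel across patients. The total angle adds two tests (one Spearman, one ANOVA); three separate axes add six.
2. For each image, compute from the six recorded values the displacement of points 10, 20 and 30 mm from the isocentre, for example the largest over a sphere of each radius, and report it beside 3DV. Where contours are available, the GTV edge can be used instead.
3. State which displacement measure the 1 mm statement in Section 6 refers to, and report the result on both 3DV and the six-value displacement. The clinical threshold itself is not changed.

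The fixed-distance version needs no new imaging and no new patients, only analysis, a few more exploratory tests and one more table. With five patients the added p-values should be read as descriptive. The GTV-edge version costs more, because it needs contour data that Section 4.1.2 does not list.

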3.3.2. Procedures

To detect intrafractional motion during treatment delivery, the ExacTrac in-room based monitoring system (Brainlab AG, Munich, Germany) is used (11, 12). It is employed in this study to repeatedly record 3D deviations of the target isocenter for both translation and rotation, during a single RT session.

Following thermoplastic mask molding, contrast-enhanced treatment planning CT is performed. CT scans are also used for image registration to reference ExacTrac recordings and CBCT-guided patient positioning at the beginning of each treatment session. Calculated 6D shifts are checked and, if indicated, translational and rotational deviations from reference positions are computed and corrected by adjusting the treatment couch (equipped with the HexaPod evo RT system, Elekta AB, Stockholm, Sweden) until translational deviation in each direction are < 1.0 mm and rotational errors are $< 1.0^\circ$.

The first ExacTrac measurement is taken before treatment start at a rotatable baseplate position of 0° . This initial ExacTrac recording is used as a reference point for comparison with the subsequent intrafractional measurements made during irradiation ($N = 3$ to 10). Patient positions are not corrected during a treatment session.

ExacTrac measurements are taken simultaneously with arc irradiations (five per RT session) at gantry angles of 0° , 90° , 180° or 270° with a tolerance range of $\pm 10^\circ$. For shaped beam application, ExacTrac recordings are taken immediately after each field application (five to eight per fraction). A final pair of ExacTrac images at a reset baseplate position of 0° are acquired at the end of each treatment session.

4. Data management

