4.1.2. Data collection and variable abstraction

The following parameters are extracted, saved in a database and analysed:

- baseplate position [$^\circ$]
- elapsed time since treatment start
- X axis translation
- Y axis translation
- Z axis translation

- X axis rotation
- Y axis rotation
- Z axis rotation
- 3D deviation is calculated from X-, Y- and Z-translation

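### The time-trend tests name no unit of analysis; if all images from five patients are pooled, the 0.05 level is not assured

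*Combined protocol and SAP*

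**What the plan says.** The Study Summary lists "Development of head deviation with time during single RT sessions" among the endpoints. Two tests serve it. Section 5 relates 3DV to "the time elapsed since the first measurement in each treatment session" and states: "Spearman's rank correlation coefficient is calculated. An analysis of variance (ANOVA) is used to analyse this correlation further". The threshold is p < 0.05. Section 5 does not name the ANOVA factor; the Study Summary does: "ANOVA Analysis of deviations in 2-minute interval groups".

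The data structure is in other sections. Section 3.2 plans 5 patients. Section 3.2.1 admits conventional and hypofractionated schedules, so a patient may have many sessions. Section 3.3.2 gives 3 to 10 images per session after the first one, and says of the first: "This initial ExacTrac recording is used as a reference point". It describes two delivery techniques, one with five arcs per session and one with five to eight fields per fraction.

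No section names a unit of analysis, a patient or session term, a repeated-measures model or a per-session summary. The extraction list in Section 4.1.2 has no patient or session number. The time origin also differs: Section 4.1.2 records "elapsed time since treatment start", Section 5 counts from the first measurement, and Section 3.3.2 says "The first ExacTrac measurement is taken before treatment start".

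**The concern.** One coefficient and one ANOVA on time groups most plainly mean that all images go into one file as independent rows. They are not independent. Images from one patient resemble each other, and all images of a session carry the same error from its reference image.

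The endpoint is a within-session question, but a pooled test also responds to differences between patients. If a patient with long sessions also has large deviations, late images show larger 3DV without anyone drifting. If drift differs between patients and averages zero, image-level counting treats the chance average of five slopes as if it came from hundreds of independent observations. In other layouts the same clustering makes the tests too cautious. A reader given p < 0.05 could not tell within-session drift from differences between patients, and these are the only tests named for this endpoint.

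**Working it through.** The plan has no sample-size or power figure to reproduce; its only stated figure is the 0.05 threshold. The question is what level the pooled tests actually hold.

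**From the documents:** 5 patients; 3 to 10 images per session after the reference; sessions of up to 20 minutes (Section 2.2); threshold 0.05.

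**Assumed, because the documents do not say:** 5 or 10 sessions per patient; sessions of 8 to 20 minutes; images evenly spaced; log 3DV = patient effect (SD 0.3) + session effect (SD 0.3) + slope × time + residual (SD 0.5); no average trend. The patient share of variance is then 0.09 / (0.09 + 0.09 + 0.25) = 0.21. With a patient SD of 0.1 it is 0.01 / (0.01 + 0.09 + 0.25) = 0.03.

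**Baseline.** With independent observations the simulated pooled tests return 5.1% (Spearman) and 4.9–5.0% (ANOVA), so the method recovers the nominal level when there is no clustering.

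**False-positive rates of the pooled tests, 5 / 10 sessions per patient:**

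| Image timing | Patient slopes | Spearman | ANOVA, 2-min groups |
|---|---|---|---|
| Identical (7 images, 14 min) | common | 2% / 2% | 0.4% / 0.4% |
| Identical | vary around zero, SD 0.02 per min | 6% / 13% | 1.2% / 3.2% |
| Varies by session, 3–10 images | common | 6% / 7% | 3% / 2% |
| Varies by session, 3–10 images | vary, SD 0.02 | 13% / 20% | 6% / 8% |
| Fixed by patient, 3–10 images | common | 13% / 23% | 9% / 23% |
| Fixed by patient, patient SD 0.1 | common | 7.4% / 5.7% | 2.6% / 4.4% |

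The figures with one decimal in rows 2 and 6 come from 1,000 runs, the others from 2,000. The Monte Carlo standard error at 5% is √(0.05 × 0.95 / 2000) = 0.5 points, or 0.7 points with 1,000 runs. With timing fixed by patient and 6 to 9 images (one per arc or field plus the final image), Spearman gives 16% / 23%. Repeat runs of the patient-fixed case reached 25%.

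**Sensitivity.** A separate simulation used a normal outcome with patient and session variance shares of 0.3 and 0.2, and 5 sessions. Spearman and ANOVA gave 1.2% and 0.4% with identical timing, 10.5% and 2.4% with timing varying by session, and 25% and 14% with timing fixed by patient. Levels below and above 0.05 occur again, and the two tests can err in opposite directions.

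**Reference image.** Its 3DV is 0 at time 0 by construction. With 7 later images it is 1 of 8 rows, so f = 0.125 of the data is tied at the lowest rank of both variables. If the rest is unrelated, the rank correlation is about 3f(1 − f) / (1 − f³) = 0.328 / 0.998 = 0.33. With 5 × 5 × 8 = 200 rows the critical value is about 1.96 / √199 = 0.14. In simulation without drift, including the reference made Spearman reject in 100% of runs and the ANOVA in 97.5–100%.

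**Patient-level alternative.** A t-test (4 df) on the five patient means of within-session rho, reference excluded, held 3.4–6.4% over 29 scenarios without average drift.

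**The case against.** The plan never says that images are pooled. The phrase on time in Section 5 and the endpoint wording both refer to the treatment session, so a coefficient per session is possible. That stands, and it makes the secure defect an unstated unit of analysis. It does not rescue the test: the text gives no way to get from many session coefficients to one p-value.

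The variances, slopes, session counts and lower limit on session length are all assumed. That stands too. The table shows that the level is not assured; it does not estimate the level in this study.

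Three stronger readings are tempting.

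- A reader might infer that pooled p-values are always too small. They are not: with identical timing and a common slope both tests are conservative, with small patient differences Spearman is near nominal, and the ANOVA can stay below 5% where Spearman exceeds it.
- A reader might infer false-positive rates above 40%. Rates of 41–44% for Spearman do appear, but only with 30 sessions for every patient and timing fixed by patient. The two techniques and the mixed schedules make patient-specific timing possible; nothing establishes it.
- A reader might infer that the reference image is analysed. Section 3.3.2 makes it the standard against which later images are compared, which suggests that it is left out. Section 5 simply does not say so.

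Finally, this is a small observational study without a power claim. But the protocol sets a significance threshold itself, and with five patients counting images can mislead badly.

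**Conclusion.** The concern holds as a gap in specification with real consequences for the time-trend p-values. On the plain pooled reading, at 5 to 10 sessions per patient and the assumed SDs of 0.3, 0.3 and 0.5, the nominal 5% for Spearman may be about 2% or about 13–25%. Differences between patients in timing or drift may inflate it; small patient differences (SD 0.1) leave it near nominal. No direction can be asserted for this study. The reference image would matter more than the clustering if it were included, though the likely intention is that it is not.

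The descriptive summaries do not depend on these tests. Section 6 ties an added margin to motion that exceeds 1 mm significantly. The documents do not settle whether that means a statistical test; if it does, the same unit of analysis should apply there. The change should be made, and it is a modest one.

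**What to change.** In Section 5:

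- State that the patient is the unit for inference and that the reference image is excluded.
- Compute Spearman's rho of 3DV on elapsed time within each session, average it per patient, and report the five patient values and their mean with a t-based 95% CI (4 df).
- Present the 2-minute groups descriptively, with the number of patients and sessions in each, and name one time origin. Within-session rho does not depend on the origin; the groups do.
- Keep coded patient and session numbers in the analysis dataset.
- If data were already collected, as enrolment in 2014–2015 and a protocol dated 2019 suggest, label the change post hoc.

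A model-based test on the 2-minute groups is not proposed. Adding only a session term to the ANOVA gave 9% and 13% false positives at 5 and 10 sessions when patient slopes vary, and richer models were not checked with five patients.

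The cost is wording, two coded variables and a by-session run in the SPSS already planned. The downside is a wider interval and lower power. For a 1.75-fold rise in 3DV over 14 minutes (slope ln 1.75 / 14 = 0.040 per minute on the log scale), with timing varying by session, power is 69–83% at 5 sessions per patient with a common slope and 55–61% if patient slopes vary (SD 0.02). At 10 sessions it is 94–98% and 70–75%. The median half-width of the CI for mean rho is 0.19–0.27 at 5 sessions and 0.14–0.22 at 10. Rho also describes the order of the images, not change per minute.
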